6.4. CEREBROSPINAL FLUID (CSF) COLLECTION

Participant will have CSF acquired via lumbar puncture (LP). In some instances, subjects would have had an LP as part of clinical evaluations or other research studies. If we obtain samples from the prior LP (within 6 months of the baseline visit) and sufficient samples are available for the molecular analysis, then baseline LP will not be necessary. Otherwise an LP will be done at baseline. All CSF samples will be collected after at least 6-hour fast from the last meal. CSF will be collected using a 24-g Sprotte atraumatic spinal needles. This needle decreases the frequency of post LP headaches to < 1%.⁷² All CSF collection is completed according to guidelines put forth in the "Biospecimens Best Practice Guidelines for the ADCs" published by the National Alzheimer's Coordinating Center (NACC) and available on their website. Approximately 30-45 ml of CSF will be collected using sterile polypropylene collection tubes. The samples will be immediately divided into aliquots and transferred for storage in a freezer for future assays.

6.5. BRAIN MRI PROTOCOLS

MRI protocols are performed in 50-60 minutes and will be conducted at the Emory Center for Systems Imaging (CSI) core. The MRI protocol includes:

(i) Structural MRI and WMH: High-resolution anatomical images will be acquired using a 3D-Fast Spoiled Gradient Recalled Echo (FSPGR) Sequence. WMH regions will be identified by a 3D T2 Fluid Attenuated Inversion Recovery (FLAIR) Fast Spin Echo sequence.

(ii) ASL-MRI: ASL images will be acquired using a custom 3D stack of interleaved spirals fast spin echo sequence and will be averaged in order to improve the signal-to-noise ratio.

(iii) Diffusion tensor imaging: DTI is highly sensitive to detect structural changes over a short time, less than 1 year, as compared to traditional MRI.⁷³

(iv) Resting state functional MRI (rs-fMRI): Resting state fMRI will be used to assess "functional connectivity" between brain regions. Functional connectivity has a key role in important complex cognitive processes.⁷⁴ It focuses on spontaneous, rather than task-induced low frequency (<0.1 Hz) fluctuations in the blood oxygenation level-dependent (BOLD) signals.

6.6. VASCULAR MEASURES

Arterial stiffness and microvascular function: Pulse-wave velocity (PWV) measured between carotid and femoral arteries is a regional assessment of aortic stiffness and is the gold standard index of arterial stiffness.

Blood pressure and Pulse-wave analysis (PWA): A brachial BP will be measured twice while seated and after 1 and 3 minutes standing according to the AHA guidelines.⁴⁵ Radial pulse wave analysis (SphygmoCor®, Atcor Medical, Australia) will be acquired as described previously.⁷⁵⁻⁷⁷

6.7. LEUKOTRIENE INHIBITION ACTIVITY

Cysteinyl leukotrienes (LTE₄) and CysLT type-1 (CysLT1) receptor activity will be assessed via single blood or urine sampling at baseline, 6 and 12 month visits by a highly selective and sensitive Liquid Chromatography/Tandem Mass Spectrometry (LC/MS/MS) method described previously.^{78,79} We will use this as a measure to assess the degree of blockade of CysLT type-1 (CysLT1) receptor activity.

6.8. BLOOD CHEMISTRIES AND BLOOD COUNT

Blood will be drawn at various visits. Please refer to **Table 1** for specific tests done at each visit.

6.9. BLOOD AND CSF BANKING

We will collect blood and CSF samples for future research. Vials containing blood samples, which will include serum, plasma and buffy coat as well as other blood products will be labeled with subject ID numbers, barcoded and stored at the cryogenic storage facility until time of processing. The label will include the study name, study visit number, contents of each collection vial, and the date of collection. The samples will be kept until the samples are exhausted. Future study results obtained from these samples may not be reported to subjects.

6.10. SCHEDULE OF EVALUATIONS

6.10.1. SCREENING

Individuals who express an interest will first participate in a screening process. During the remote (phone/virtual) or in-person screening visit, after informed consent has been obtained either on paper or electronically, we will collect demographic and medical information, and perform a series of tasks to determine subject safety and eligibility to participate in the study e.g. blood pressure checks, cognitive testing, lab testing. See Table 1 for detailed information on study procedures performed at screen visit.

Participants meeting eligibility criteria detailed in Section 4 (Selection and enrollment of participants) will be scheduled for the baseline visit.

6.10.2. ENROLLMENT, BASELINE, AND FOLLOW-UP

Once eligible, baseline evaluation will be completed. A clinical evaluation and LP will be done during the baseline visit, unless one was done earlier during screening. Biospecimens will be collected for inflammatory and endothelial markers. Once baseline data are collected, participants will be randomized into Montelukast or placebo. During the medication escalation period, participants will be monitored via follow-up phone calls every 2 weeks until max dose is achieved, or participant reports adverse events (see intervention for issues related to increased LFT). Participants will return for follow-up visits at 6 weeks post-randomization, and at 3, 6 and the final 12-month visit. Blood pressure, heart rate, weight, laboratory testing, adverse events (AE) or serious adverse events (SAE), pill count (to assess compliance), and use of non-study medications data will be collected for frequent monitoring. At least 1 follow-up phone call will also occur between 6 and 12 months. An optional modified phone/virtual visit will be completed as needed for any visit to collect data that can be reasonably collected by phone. This change is in response to the COVID-19 stay home orders. However, subjects will be given the option to continue doing portions of the visits virtually when normal business operations resume. All visits will have a +/- three-week window for subjects to reschedule as needed, except for the 6-week visit which will have a +/- one-week window. Study procedures and timeline are shown in **Table 1**.

7. SAFETY ASSESSMENTS

7.1. SPECIFICATION OF SAFETY PARAMETERS

(i) The following safety parameters are related to the use of Montelukast: The finding of an elevated ALT, AST, or bilirubin ($> 3 \times \text{ULN}$) or other clinical evidence of liver disease such as jaundice, encephalopathy. Headache, stomach cramps, fever, nasal congestion, upper respiratory tract infection and throat irritation are less common side effects.

Other infrequent side effects of Montelukast include runny nose, diarrhea, dizziness, fatigue, joint or muscle pain, bronchitis, gastroenteritis, pancreatitis, rash, dental pain, and ear or skin disorders. Angioedema, eosinophilia, vasculitis, increased bleeding tendencies, seizures, altered behavior and suicidal thoughts are also rare but potential complications of Montelukast.

(ii) The following safety parameters are related to the conduct of the study procedures: Neuropsychological assessment may be accompanied by anxiety, frustration and overall fatigue. The attachment and removal of a blood pressure cuff, cuffs for venous occlusion, and ultrasound probe on the neck may cause mild discomfort. Brain imaging requires the participant to stay still and lie down for 50-70 minutes, which may cause boredom and minimal reversible back pain. Because of the closed space and noise, undergoing an MRI may be associated with anxiety or panic reactions. The vascular ultrasound is safe and only mildly uncomfortable due to discomfort in the arm when the cuff is inflated. We will use ultrasound to painlessly bounce sound beams off the carotid artery using a pencil-like sensor.

(iii) The following safety parameters are related to the LP procedure: The most common complication of a lumbar puncture is post-LP headache. We use a smaller 24-gauge Sprotte spinal needle. All subjects will be counseled on the signs and symptoms of post-LP headaches and given information on management (acetaminophen, caffeine, rest). Bacterial meningitis and a CSF leak are very rare complications of lumbar punctures. A blood patch is rarely needed to heal CSF leaks. All subjects will be instructed to promptly contact us if the headache persists beyond 3 days and if a blood patch is required, the cost of the patch will be covered by the funds supporting this project.

7.2. METHODS FOR ASSESSING AND RECORDING SAFETY PARAMETERS

During the study, any problem reported by the participants will be recorded in the participant's research record (adverse event log), along with the start and stop dates. The problem may be related to the research participation or the drug used in the study (drug reaction). All adverse events will be rated on the following characteristics:

(i) Serious (YES/NO): A serious adverse event (SAE) is defined using the Code of Federal Regulations Title 21 definition as any event that results in any of the following outcomes: Death, a life-threatening adverse event, inpatient hospitalization or prolongation of existing hospitalization, a persistent or significant incapacity or substantial disruption of the ability to conduct normal life functions, or a congenital anomaly/birth defect.

(ii) Related to the research: All adverse events will be judged regarding their relationship to the research participation or the study drug as related, possibly related, probably related, unrelated, or unknown.

(iii) Severity: The severity of the AE will be rated on the following scale mild, moderate, severe, life-threatening, or death.

(iv) Anticipated or unanticipated: We use the Emory IRB definition of an unanticipated event as any event that is "unexpected, not described in the study documents, or if described before, it is now presenting with increased severity, duration, or frequency".

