4. SELECTION AND ENROLLMENT OF PARTICIPANTS

4.1. INCLUSION CRITERIA

- (1) Age: 50 years or older;
- (2) MCI group will be defined based on:

- (i) Subjective memory concern;
- (ii) Abnormal memory function documented using the Logical Memory subscale (Delayed Paragraph Recall, Paragraph A only) from the Wechsler Memory Scale-Revised (the maximum score is 25): [<11 for 16 or more years of education; <9 for 8-15 years of education; <6 for <7 years of education];
- (iii) Montreal Cognitive Assessment (MoCA) < 26;
- (iv) Clinical Dementia Rating scale /Memory box score=0.5;
- (v) General functional performance sufficiently preserved (Functional Assessment Questionnaire ≤ 5).

(3) *Early AD dementia* group will be defined based on:

- (i) Subjective memory concern;
- (ii) Abnormal memory function documented using the Logical Memory subscale (Delayed Paragraph Recall, Paragraph A only) from the Wechsler Memory Scale-Revised (the maximum score is 25): [<11 for 16 or more years of education; <9 for 8-15 years of education; <6 for <7 years of education];
- (iii) Montreal Cognitive Assessment (MoCA) <26;
- (iv) Clinical Dementia Rating scale/Memory box score 1 or 2;
- (v) Early AD dementia defined as Functional Assessment Staging Test (FAST) of 4 or 5;

In instances where the diagnosis of early AD is not clear, a review of the subject's cognitive and non-cognitive data will be performed by the study physicians or neuropsychologists and a diagnosis of the degree of cognitive impairment will be based on the clinical judgment of the study physicians or neuropsychologists.

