5. STUDY INTERVENTIONS

5.1. INTERVENTIONS, ADMINISTRATION, AND DURATION

Participants will be randomized to either Montelukast or placebo in a 1:1 fashion. All participants will be initiated on 10 mg. The dose will be increased in 2-week increments to 20 mg and 40 mg as long as participants report no intolerable symptoms or adverse events (e.g. jaundice, headache, GI symptoms, and neuropsychiatric changes), and liver enzymes checked at 6 weeks do not exceed 3X baseline levels. If participant had positive LFT change (3x increase), dose will be decreased to the prior level (20 mg or matched placebo) and LFT rechecked 2 weeks later. If LFT increases further, then dose will be decreased to 10 mg or matched placebo. If LFT are still increased 2 weeks after 10 mg or matched placebo, study medication will be discontinued. Treatment will be provided in similar capsules format to be taken orally 1-2 times a day. Investigators, study personnel and participants will be blinded for drug assignment. Participants will be treated for 1 year.

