7.4. FOLLOW-UP FOR ADVERSE EVENTS

All AE/SAE will be recorded in the participant chart with start/stop date. The study physician may perform additional evaluations, unscheduled visits, phone communication, repeat blood testing, or refer to the emergency room or the participant healthcare provider for medical care if necessary. If the event results in intervention discontinuation (>5 months) but not study withdrawal, the participant will be followed as defined in the study. They will also be invited to perform the final visit evaluation including all study procedures planned for that visit if the participant has been in the study for more than 5 months post-baseline evaluation.

When a subject notifies the study team that they have symptoms suggestive of a treatment-emergent AE/SAE, the study physician will review the incident and determine if the subject is safe to continue in the study. The physician may discontinue the study medication immediately, elect to lower the dose of the study medication, ask subject to present to the study center for a safety evaluation, and/or monitor the subject's concern. The subject may continue in the study if on the lower dose of the study medication, they experience some resolution of symptoms. In those on 20 mg and 40 mg, the doses will be decreased to the next lower dose. In those on 10 mg of Montelukast, a trial of every other day 10 mg of Montelukast will be attempted prior to discontinuation.

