When there are two or more available persons who are in different orders of priority pursuant to subdivision (c), refusal to consent by a person who is a higher priority surrogate shall not be superseded by the consent of a person who is a lower priority surrogate. That surrogate will need to consent to the study. If either party refuses, we do not enroll the subject. To ensure both the participant and the proxy understand the study protocol, we will ask subjects or legal next of kin to explain in their own words the nature of the study and the procedures involved.

The proxy will be considered the study informant if there is contact at least once a month. In some instances, such as the lack of adequate contact by the surrogate or the surrogate's inability to complete the tasks of the study informant, the study informant may be a different individual as long as he/she is willing to provide information about the participant and have contact with the participant for at least once a month (in person or telephone). The study informant will sign the study informed consent. If they are not available in person, the study staff will contact the informant to obtain needed information about the subject cognitive symptoms. In that case, a verbal consent will be obtained.

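### Symptom adverse events are described as coming from participant report in a memory-impaired sample, with no informant query or structured elicitation specified; under-reporting is likely, by an unknown amount

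*Combined protocol and SAP*

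**What the plan says.** Four places in the protocol describe where symptom reports come from, and each names the participant.

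- Section 7.2 (recording of safety parameters): "any problem reported by the participants will be recorded" in the adverse event log, with start and stop dates.
- Section 5.1 (escalation): the dose rises "as long as participants report no intolerable symptoms or adverse events", and provided that "liver enzymes checked at 6 weeks do not exceed 3X baseline levels".
- Section 6.10.2 (escalation calls): participants are phoned every 2 weeks until they reach the maximum dose or report an adverse event.
- Section 7.4 (physician review): "When a subject notifies the study team that they have symptoms suggestive of a treatment-emergent AE/SAE", the study physician reviews the incident.

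Section 6.10.2 also lists AE/SAE among the data collected in follow-up, without saying from whom or how.

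On the sample, section 4.1 requires for both the MCI and the early dementia group "Abnormal memory function documented using the Logical Memory subscale". The dementia group has a CDR memory box score of 1 or 2. Section 4.2 excludes MoCA scores of 10 or below and lets people without capacity enrol through a study partner or surrogate.

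On the informant, section 6.3 has an informant or study partner questioned for the CDR. Section 11.2 asks for contact with the participant at least monthly. Where the informant cannot attend, "the study staff will contact the informant to obtain needed information about the subject cognitive symptoms". Adverse events are not mentioned.

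**The concern.** The person named as the source of symptom reports is the person whose memory impairment is the reason for enrolment. Someone who sees or speaks to the participant regularly is already part of the trial but is not asked. GI symptoms, behavioral changes and treatment-emergent events are listed as safety outcomes in Table 2, and 7.2 needs dates for each event.

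Contacts also thin out. After the 3-month visit the next visits are at 6 and 12 months, with a minimum of one call between those two.

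If symptoms are forgotten, event rates come out too low in both arms, absolute differences shrink, and a report of no events says less than it appears to. An unreported symptom cannot be recovered after the data are collected. In a trial with safety in its primary objective and 15 completers per arm, that weakens what it can claim about tolerability.

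**Working it through.** The plan gives no expected adverse event rate, no capture rate and no power for a safety comparison, so there is no figure to reproduce. The check has two parts.

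**1. Which safety data depend on participant report**

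| Data | Dependent on participant report? | Section |
|---|---|---|
| GI symptoms, headache and similar | Yes, as described | 7.2, 7.4, Table 2 |
| Symptom part of the escalation criterion | Yes | 5.1, 6.10.2 |
| Liver enzymes and other safety labs (6 weeks; 3, 6, 12 months) | No | Table 1 footnotes |
| Discontinuations, deaths | No | Table 2 |
| Behavior, suicidality | Partly: NPI-Q and S-STS are given | 6.3 |

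NPI-Q and S-STS have no row of their own in Table 1. If they belong to the cognitive battery, they fall at baseline, 6 and 12 months, outside escalation.

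The liver criterion in 5.1 does not clearly precede the last dose step. "The dose will be increased in 2-week increments to 20 mg and 40 mg", read literally, puts 10 mg at week 0, 20 mg at week 2 and 40 mg at about week 4. The enzyme check is at 6 weeks, or week 5 at the earliest under the one-week window in 6.10.2.

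**2. What under-capture would do (illustration)**

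From the documents: 36 enrolled at 1:1 (sections 3 and 5.1), so 36/2 = 18 per arm. Assumed: true incidence *p*, and a probability *c* that a participant's event is recorded, equal in both arms.

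Chance of recording no event in an arm: (1 − *pc*)^18. For *p* = 0.15:

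- *c* = 1: 0.850^18 = 0.054
- *c* = 0.8: 0.880^18 = 0.100
- *c* = 0.5: 0.925^18 = 0.246

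The same formula over a range of incidences:

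| True incidence | *c* = 1 | *c* = 0.8 | *c* = 0.5 |
|---|---|---|---|
| 5% | 40% | 48% | 63% |
| 10% | 15% | 22% | 40% |
| 15% | 5% | 10% | 25% |
| 20% | 2% | 4% | 15% |

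If no event is recorded in 18, the 95% upper bound on the true rate is (1 − 0.05^(1/18))/*c*. This gives 0.153 at *c* = 1, 0.153/0.8 = 0.19 at *c* = 0.8, and 0.153/0.5 = 0.31 at *c* = 0.5.

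The observed risk difference is *c* times the true one: a true 20 points appears as 16 (*c* = 0.8) or 10 (*c* = 0.5). The risk ratio is *pc*/*qc* = *p*/*q*, which does not change.

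For true rates of 50% against 10%, two-sided Fisher exact power with 18 per arm is 67% at *c* = 1, 47% at *c* = 0.75 and 25% at *c* = 0.5. With equal true rates of 20%, the rejection rate is 2.05% at *c* = 1 and 0.92% at *c* = 0.5. Equal under-capture costs sensitivity and does not create false differences.

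**The case against.** The strongest reply is that the protocol does not say participant report is the only source. Section 7.2 says what is recorded and does not exclude other routes. Section 7.4 says all AE/SAE are recorded without naming a source, and 6.10.2 leaves the method open. Section 10.1 refers to trial-specific forms, which may contain a symptom list. Section 11.2 describes the informant as someone willing to give information about the participant, without limiting the subject. Delayed paragraph recall is also not a measure of how well someone reports nausea, MCI participants must have largely preserved function (FAQ of 5 or less), and the calls during escalation are only 2 weeks apart.

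Much of this stands, and it rules out several stronger readings. A reader might infer:

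- That all safety data rest on recall. They do not: laboratory results, discontinuations and deaths are separate, and two scales partly cover behavior and suicidality.
- That events will certainly be under-counted, or by a known amount. No document gives a capture rate.
- That the effect flatters Montelukast over placebo. In a randomized, blinded trial it would do so only if the drug changed recall or reporting, and nothing in the documents shows that.
- That the informant is barred from reporting events. The text is silent, which is not a restriction.

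The reply does not supply the missing specification. Wherever a source of symptom reports is named, it is the participant, and neither an informant query nor a method of asking is set out. The short interval between escalation calls helps there but not in the later months.

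**Conclusion.** The point holds as a gap in ascertainment for symptom adverse events. In this sample, under-reporting is likely and its size is unknown. Its effect would be lower event rates and smaller absolute differences in both arms, and a weaker basis for concluding that no events occurred. It would not by itself favour an arm, and relative measures would be unchanged under equal capture.

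The 5%, 10% and 25% figures rest on an assumed 15% incidence and an assumed capture range of 50% to 80%, set against full capture. They show how sensitive a zero count is in an arm of 18 and do not predict what this trial will find. Confidence is medium, because the case report forms are not available and might close part of the gap.

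**What to change.** In section 7.2, replace the single-source sentence with text along these lines:

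> Problems reported by the participant or by the informant/study partner will be recorded. At each scheduled call and visit, in both arms, staff will ask the participant a fixed list of the symptoms in Table 2, and will ask the informant the same list where there is one. The source of each event (participant, informant, both, other) will be recorded.

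Headache appears in 5.1 and 7.1 but is not itemized in Table 2, so the authors should decide whether to add it to the list. Add to section 9.3 that symptom events will be reported by arm and by source. Add rows to Table 1 for NPI-Q and S-STS so that their timing is clear.

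For sections 5.1 and 6.10.2, no escalation rule is proposed here. The authors should state whose report informs the escalation calls, and should reconcile the 6-week liver enzyme check with the 2-week dose steps.

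The cost is one paragraph, a one-page form and a few minutes per contact, including the added informant contact. More minor events will be logged in both arms. Section 11.2 expressly requires an informant only when the UBACC score is below 14.5, so two-source capture may not reach everyone; reporting by source makes that visible.

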7.3. REPORTING ADVERSE EVENTS AND DEATH

All adverse events will be assessed for the need for prompt reporting. We follow the guidelines set forth by the Emory IRB for reporting AEs. Any event that fulfills the following criteria being unanticipated (as defined in section 7.2), probably or possibly related to study participation (drug effect or as a consequence of a study procedure), and involving risk for participants or others is considered an unanticipated problem and will be reported to the Emory IRB within 10 days. If an event could be explained by the underlying medical condition, it is not considered related and hence not reportable. Any SAE as defined in **section 7.2** that does not fit all the criteria of being an unanticipated problem will be reported during continuing review. Deaths of participants during the study will be promptly reported to the IRB if related to study participation and reported during continuing review if they are not related to study participation.

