9.3. DATA ANALYSIS

Table 2 provides a list of main outcomes.

Table 2. Independent, main outcome and other variables to be used in the analyses	
Independent:	Group (Montelukast vs placebo)
Safety outcome:	GI symptoms (diarrhea, nausea, vomiting), anaphylaxis, elevated liver enzymes, PT/INR, behavioral changes, seizures, number of discontinuations from Montelukast, treatment-emergent AE/SAE, deaths
CSF outcomes:	CSF amyloid and tau, inflammatory proteins
Vascular outcomes:	PWV/PWA
Imaging outcomes:	Perfusion, hippocampal volume
Cognitive outcomes:	CDR, NIH Toolbox Cognition battery (NIHTB-CB)

Baseline characteristics including demographic, social and cognitive measures will be compared between the 2 groups to assess randomization fidelity. The list of the main variables is shown in Table 2. We will compare the change in our outcomes over the study period between the treatment and placebo arms using Mixed Models. For the dose response analysis, the dose vs cysLT-1 receptor activity will be plotted to explore the degree of cysteinyl leukotriene modulation at the various doses.

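### The SAE definition in section 7.2(i) has five outcomes and no medically important category, so a seizure, suicidal behaviour, anaphylaxis or clinical liver injury that is not life-threatening, disabling or admitted is rated non-serious, although the plan singles these events out

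*Combined protocol and SAP*

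**What the plan says.** Section 7.2(i) has every adverse event rated serious, yes or no. An SAE "is defined using the Code of Federal Regulations Title 21 definition", which the section then spells out as "any event that results in any of the following outcomes: Death, a life-threatening adverse event, inpatient hospitalization or prolongation of existing hospitalization", followed by "a persistent or significant incapacity or substantial disruption of the ability to conduct normal life functions, or a congenital anomaly/birth defect". The list ends there.

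Other sections mark certain events as ones to watch:

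- **Section 7.1** says that "seizures, altered behavior and suicidal thoughts are also rare but potential complications of Montelukast". It opens the drug-related parameters with "The finding of an elevated ALT, AST, or bilirubin" above three times the upper limit of normal, or other clinical evidence of liver disease, with jaundice as an example.
- **Section 6.3** includes the S-STS to monitor suicidal ideation and behaviour during treatment.
- **Section 8** gives seizures (item 4) and hepatic disease (item 5) among the possible grounds for stopping the intervention or withdrawing the participant.
- **Table 2 in section 9.3** has among its safety outcomes "anaphylaxis, elevated liver enzymes, PT/INR, behavioral changes, seizures, number of discontinuations from Montelukast, treatment-emergent AE/SAE, deaths".

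For handling, section 7.4 lets the study physician "refer to the emergency room or the participant healthcare provider for medical care if necessary". For reporting, section 7.3 sends to the Emory IRB within 10 days "Any event that fulfills the following criteria being unanticipated (as defined in section 7.2"), provided that it is also at least possibly related and involves risk. An SAE that does not meet all of those conditions goes to continuing review. Under 7.2(iv), an event already described counts as unanticipated only if its severity, duration or frequency has increased.

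**The concern.** Safety comes first in the primary objective. The plan identifies a short list of events that matter for this drug, but the rule that decides what is serious does not refer to that list. It looks only at outcome. An event can therefore be grave enough to be a ground for stopping study drug under section 8 and still be recorded as non-serious.

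Two things are at stake. The first is the SAE count, which readers of a small safety trial look at early. The second is IRB reporting. Section 7.3 uses the 7.2 definition to decide what reaches continuing review, so an event outside that definition, and not unanticipated either, has no named route. Borderline cases would also depend on how freely a rater applies the life-threatening or disruption criteria, and that may differ from one event to the next.

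**Working it through.** No arithmetic applies, so the check compares the passages.

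**Step 1. Count the outcomes in 7.2(i).** There are five: (a) death; (b) a life-threatening event; (c) inpatient or prolonged hospitalization; (d) lasting or significant incapacity, or substantial disruption of normal functioning; (e) congenital anomaly. No other section adds a criterion or makes any event serious by its nature.

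**Step 2. Test each event against the list.** Take a non-fatal event managed without admission, for example by the emergency-room referral that section 7.4 allows. Outcomes (a), (c) and (e) do not apply. Outcomes (b) and (d) remain, and neither needs admission.

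| Event | Where the plan singles it out | Serious without admission if | Otherwise |
|---|---|---|---|
| Seizure | 7.1, section 8(4), Table 2 | (b) or (d) is met | non-serious, e.g. brief and self-limited |
| Suicidal behaviour | S-STS in 6.3 (7.1 names thoughts only) | (b) or (d) is met | non-serious, e.g. an act without danger to life |
| Anaphylaxis | Table 2 | (b) or (d) is met | non-serious, e.g. a treated reaction not judged life-threatening |
| Clinical liver injury | 7.1, section 8(5); enzymes in Table 2 | (b) or (d) is met | non-serious, e.g. jaundice managed as an outpatient |

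The gap is therefore the set of events that meet neither (b) nor (d) and are not admitted.

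**Step 3. Follow such an event through 7.3.** Take a first seizure, or jaundice, of ordinary severity.

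- *10-day route.* This needs the event to be unanticipated. Both are described in 7.1, so under 7.2(iv) they normally are not.
- *Continuing review.* For non-fatal events, section 7.3 specifies this for SAEs as defined in 7.2. The event is not one.
- *What remains.* Only the general statement that Emory IRB guidelines are followed. Their content is not in the documents.

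The result is less certain for the other two. Section 7.1 does not name anaphylaxis, although Table 2 does. A suicidal act may count as increased severity over the suicidal thoughts named in 7.1. Either could be unanticipated and, if at least possibly related and involving risk, would take the 10-day route.

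**Step 4. Check what is not affected.** All problems that participants report go into the adverse event log (7.2). Table 2 lists seizures, anaphylaxis and elevated liver enzymes as outcomes in their own right, whether or not they are flagged serious. Suicidal behaviour has no entry of its own there. The nearest is behavioural changes, together with the S-STS data.

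**The case against.** The strongest reply is that little of the safety evidence depends on the serious flag. The events are logged, three of the four types are covered by separate outcomes in Table 2, the S-STS tracks suicidality, and the section 8 grounds apply whether or not an event is called serious. All of that stands, and it confines the point to classification and reporting. It does not make a non-admitted seizure an SAE.

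The plan also cites Title 21 and the Emory IRB guidelines, and either might contain more than the protocol reproduces. Neither text is available here, so nothing above rests on whether the list matches them. A rater will work from the list as written, and that list is closed.

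Some stronger readings are tempting, and the documents do not support them:

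- *Anything managed without admission is non-serious.* Two of the five outcomes do not depend on admission, so anaphylaxis or a suicidal act that endangered life is already an SAE.
- *The safety comparison misses these events.* Table 2 names most of them separately.
- *A sixth criterion would bring prompt reporting.* The 10-day route does not depend on seriousness. An admitted, plainly serious seizure judged anticipated would also wait for continuing review.
- *The size can be read from the share of an arm that one participant makes up.* That share is the same for any misclassified event. The plan gives no event rates and defines no comparison of SAEs alone.

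**Conclusion.** The point holds in a limited form. The serious flag in 7.2(i) rests on five outcomes and excludes medically important events that are not life-threatening, disabling or admitted, including event types that the plan itself singles out. For a seizure or jaundice of ordinary severity, section 7.3 then names no specific IRB route, prompt or periodic.

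The consequence falls on the serious flag, the SAE count and IRB reporting. The named between-arm safety outcomes are not lost. Suicidal behaviour is the least protected of the four in the analysis, because Table 2 gives it no entry of its own. No numerical size can be attached.

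The conclusion assumes that raters apply the list as printed and that the Emory IRB guidelines, which are not in the documents, add no reporting route that would close the gap. It is worth correcting because safety is a primary objective and the correction is cheap.

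**What to change.** Add a sixth criterion to 7.2(i): a medically important event that, in the study physician's judgment, endangers the participant or needs intervention to prevent one of the listed outcomes. State next to it that seizure, suicidal behaviour, anaphylaxis and clinical hepatic disease are always recorded as serious, in both arms. The judgment then applies to all other events, including a rise in liver enzymes without clinical disease, while the four named types do not depend on it.

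Because 7.3 refers back to the 7.2 definition, these events would then reach at least continuing review without a further change to that section. They would also count as SAEs in the treatment-emergent AE/SAE entry of Table 2, which should be tabulated by arm.

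Whether anticipated events of these types should also be reported within 10 days is a separate question about 7.2(iv) and 7.3. It touches the IRB's own definition of unanticipated and need not be settled for this change.

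The cost is a sentence or two in 7.2(i), a tick-box on the adverse event form, and a few more SAE reports in a trial that plans to enroll 36 participants.
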